8.1 Sample Size

Sample size in the Phase 1b study is based on operational consideration.

The sample size in the Phase 2 study is based on the primary endpoint, SRI-4 Response at Day 210. Approximately 156 additional patients will be randomized in a 2:1 ratio to BOS161721 versus placebo to achieve 132 evaluable subjects in the FAS. This assumes 24 subjects will drop prior to having received treatment and an evaluable post-baseline efficacy measure. Enrollment and randomization will be monitored in a blinded fashion and increased if needed to ensure at least 132 subjects are randomized into the FAS.

A total of 132 subjects randomized provides more than 80% power to detect a treatment difference of 25% in SRI-4 response rates at Day 210, based on a targeted 2-sided significance level of 10% and using a 2-sided Pearson's chi-squared test. This assumes of a response rate of 65% for BOS161721 and 40% for placebo, where missing data at Day 210 is carried forward

from most recent non-missing result and subjects are treated as a non-responder if a prohibited medication defined as a medication failure occurs.

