8.2 Statistical Methods

8.2.1 Analysis Populations

The primary efficacy analysis will be based on the FAS, defined as all patients who receive at least 1 dose of study treatment and at have least 1 evaluable post-baseline efficacy evaluation. FAS analyses will be conducted on the basis of the randomized treatment.

A per protocol (PP) analysis set may be defined to exclude major protocol violations from the efficacy analysis. The PP Population will include all patients from the FAS except those with major violations to the protocol deemed to impact the analysis of the primary endpoint. These violations will be identified based on blinded data prior to study unblinding. PP analyses will be conducted on the basis of the randomized treatment.

Safety analyses will be based on the safety analysis set (SS), defined as all patients who receive at least 1 dose of study treatment. Safety analyses will be conducted on the basis of actual treatment received.

Pharmacokinetic analysis will be conducted on the PK analysis set, defined as the FAS with sufficient concentration data for the calculation of PK parameters.

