8.2.3 Primary Efficacy Endpoint(s)

The proportion of patients who achieve a SRI-4 response at Day 210 will be assessed via Pearson's chi-squared analysis. The primary efficacy endpoint will be analyzed using the FAS and if needed repeated in the PP analysis set. Missing values will be addressed by employing a last observation carried forward (LOCF) analysis. Other imputation methods may be employed as a sensitivity analysis and will be described in the SAP. Additional analyses exploring impact of baseline factors such as baseline disease severity, race, and other characteristics may be performed.

Patients that received prohibited medications or unallowable CS usage as described in [Section 4.6](#) will be considered "medication failures" and will be treated as non-responders for the primary efficacy analysis. Patients that received an allowable CS burst but having missing data at Day 210 will considered a medication failure and will be treated as non-responders for the primary efficacy analysis. The determination of medication failures will be reviewed using blinded data and finalized prior to unblinding.

The superiority of BOS161721 relative to placebo will be evaluated. If the proportion of SRI-4 responders for the selected POC dose in BOS161721 arm is higher than that of the placebo arm, then BOS161721 will be considered superior to placebo if the 2-sided p-value is less than or

equal to 0.10. Secondary and exploratory endpoints for this POC study will be evaluated based on the same statistical hypothesis.

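### LOCF in the primary analysis lets patients who leave early with a response count as Day 210 responders, while leavers who had an allowed steroid burst count as non-responders

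*Protocol*

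**What the plan says.** Protocol Section 8.2.3 tests SRI-4 response at Day 210 with Pearson's chi-squared test on the FAS. For missing data it says: "Missing values will be addressed by employing a last observation carried forward (LOCF) analysis". Section 8.1 builds the same rule into the power assumption. Other imputation methods are optional and left to the SAP.

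Two groups are exempt from LOCF. Users of prohibited medication or unallowable steroids are medication failures and count as non-responders. The second exemption reads: "Patients that received an allowable CS burst but having missing data at Day 210 will considered a medication failure". These patients also count as non-responders. The wording does not depend on arm, and medication failures are settled on blinded data.

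Section 8.2.1 gives the FAS as "defined as all patients who receive at least 1 dose of study treatment and at have least 1 evaluable post-baseline efficacy evaluation". Section 8.1 plans for the loss this causes: "Approximately 156 additional patients will be randomized in a 2:1 ratio to BOS161721 versus placebo to achieve 132 evaluable subjects in the FAS", and "This assumes 24 subjects will drop prior to having received treatment and an evaluable post-baseline efficacy measure".

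**The concern.** The endpoint is a status at Day 210. Under the stated rules, a patient who leaves with a response at the last visit is a Day 210 responder on a result never observed at Day 210, unless that patient is a medication failure or had a burst. A leaver with the same last result and an allowed burst is a non-responder. Two kinds of drop-out with equally unknown Day 210 status are thus scored in opposite ways. Dosed patients who leave before any evaluable efficacy visit are not scored at all.

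Drop-out, the response held at the last visit and burst use all arise after randomisation. If any of them differs by arm, the primary comparison moves for reasons other than response at Day 210. The test already runs at two-sided 0.10, so there is little room for further false-positive risk.

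The sponsor's own rationale sharpens the point. Appendix 7 explains the removal of the futility analysis by calling response data from before week 24 the least reliable, because placebo response is high then. LOCF can bring those same data into the primary result.

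**Working it through.** **Inputs from Section 8.1.** Test and level: "based on a targeted 2-sided significance level of 10% and using a 2-sided Pearson's chi-squared test". Rates: "This assumes of a response rate of 65% for BOS161721 and 40% for placebo", stated as already including LOCF and the medication-failure rule. Allocation is 2:1, so 132 is 88:44 and 156 is 104:52. Expected outside the FAS: 24/156 = 15.4%. The document gives no drop-out rate after the first efficacy visit and no burst rate by arm, so these are assumed below and shown as ranges.

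**1. The plan's own figure.** Section 8.1 says "A total of 132 subjects randomized provides more than 80% power to detect a treatment difference of 25" percentage points. With p̄ the pooled rate:

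Power = Φ[(|p₁ − p₀| − 1.645 × SE₀) / SE₁], where SE₀ = √[p̄(1 − p̄)(1/n₁ + 1/n₀)] and SE₁ = √[p₁(1 − p₁)/n₁ + p₀(1 − p₀)/n₀].

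- p̄ = (88 × 0.65 + 44 × 0.40)/132 = 0.567
- SE₀ = 0.0915 and SE₁ = 0.0897
- (0.25 − 1.645 × 0.0915)/0.0897 = 1.11, so power is 86.6% (86.3% by exact enumeration of the test)

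The stated power reproduces for the rates assumed under LOCF.

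**2. A gap in carried response, no true effect.** Take 40% response in both arms, drop-out d = 15% in both arms, and g = active minus placebo response carried forward by leavers. Bias = d × g. Null SE = √[0.40 × 0.60 × (1/88 + 1/44)] = 0.0905. Chance of a false superiority claim = P(Z > 1.645 − bias/0.0905).

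- g = 0: bias 0, 5%
- g = +10 points: bias 1.5 points, 7%
- g = +20 points: bias 3.0 points, about 9.5%
- g = +35 points: bias 5.25 points, 14%
- g = −20 points: bias −3.0 points, 2.4%

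**3. The burst exception alone, no true effect.** Assume 20% drop-out per arm and 40% carried response in both arms. Arm rate = 0.80 × 0.40 + 0.20 × (1 − b) × 0.40, where b is burst use among leavers. False superiority by exact enumeration (4.9% at 40% in both arms):

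- equal use (20% in each arm): 4.9%
- 10% active, 30% placebo (39.2% vs 37.6%): 7.0%
- 10% active, 50% placebo (39.2% vs 36.0%): 9.7%
- 30% active, 10% placebo (37.6% vs 39.2%): 3.4%

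**4. Unequal drop-out alone.** Suppose 32% of each arm respond at Day 210 with missing counted as non-response, and leavers carry 40%. Drop-out of 20% active and 10% placebo gives LOCF rates of 0.32 + 0.20 × 0.40 = 40% and 0.32 + 0.10 × 0.40 = 36%, and an 11.3% chance of a superiority claim. With the drop-out rates reversed it is 1.8%.

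**5. Power when dosed patients outside the FAS are added as non-responders.** If k of the 24 were dosed, split 2:1, the rates become 57.2/(88 + 2k/3) and 17.6/(44 + k/3).

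- k = 6: 85.1%
- k = 12: 83.6%
- k = 18: 82.3%
- k = 24 (55.0% vs 33.8%): 81.1%

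**6. Power when later drop-outs also count as non-responders.** Multiply both rates by (1 − d), with d equal in both arms and leavers assumed to carry response at the same rates as completers. The higher figure has none of the 24 dosed (132 analysed); the lower has all 24 dosed (156 analysed).

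- d = 5%: 83.2% to 77.7%
- d = 10%: 79.3% to 74.1%
- d = 15%: 75.3% to 70.4%
- d = 20%: 71.0% to 66.5%

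**The case against.** A reader might infer that the burst rule works against placebo, since bursts are given for disease activity, and so that the plan favours the active arm. The documents do not support that. The rule is worded alike for both arms and applied blinded, and no burst or drop-out rate by arm is given. The high early placebo response cited in Appendix 7 would also be carried forward, which pushes the other way. The 14% figure needs an assumed 35-point gap and is one scenario among several.

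Nor may the 24 patients be read as 24 dosed patients discarded. Section 8.1 mixes never-dosed patients with dosed patients who have no post-baseline measure, and does not give the split.

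Other points also have weight. Section 8 promises to assess the effect of discontinuation and withdrawal. Many exits for lack of efficacy may already be non-responders through the medication-failure rule. The appended Version 2.0 protocol (Section 6.5) asks for an end-of-treatment visit on withdrawal, so the carried value may be the status at exit; the corresponding current section is not shown. The trial is a proof of concept, and its power statement is correct as declared.

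These points limit the size of the problem but do not remove it. Status at exit is still not status at Day 210, and the protocol makes LOCF the primary rule while alternatives stay optional.

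**Conclusion.** The concern holds as a weakness in a stated rule, not as an arithmetic error and not as a bias of known direction. LOCF can make early leavers Day 210 responders, the burst exception scores comparable leavers the other way, and the FAS drops some dosed patients.

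The effect depends on arm differences that the document does not quantify. In the assumed scenarios at 15% drop-out with no true effect, the false-superiority risk is 5% with no gap, 7% to 14% when active leavers carry 10 to 35 points more response, and about 2% when placebo leavers carry 20 points more. The present margin over 80% power depends partly on responses that would not be observed at Day 210.

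**What to change.** In Section 8.2.1, define the primary set as all randomised patients who received at least one dose. In Section 8.2.3, count any missing Day 210 SRI-4 as non-response, with or without a burst; the plan already does this for burst users. Commit to LOCF on the current FAS as a sensitivity analysis. In Section 8.1, restate the assumed rates and the power on that basis, with the expected drop-out and the split of the 24 patients into dosed and never dosed.

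The cost is wording in three sections and lower stated power. Adding the dosed patients alone keeps power at 81% to 85% if 6 to 24 of the 24 were dosed. Counting later drop-outs as non-responders as well takes it below 80% from about 10% drop-out, so the claim of more than 80% cannot stand unqualified. No extra patients or visits are asked for. Section 8.1 already allows a blinded increase in enrolment, tied to the FAS count, should the sponsor wish to recover the margin.

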8 STATISTICS

The following analyses are planned:

- An IA will be performed during the last cohort of the MAD phase to determine dose selection for the POC phase.
- The final analysis will be performed when all patients have completed the safety follow-up or withdrawn from the study.
- Safety analyses will be performed for DMC reviews throughout the study to evaluate dose escalation decisions and accumulating safety data. The frequency and details of the

content and format of the safety review meetings will be described in the SAP and/or DMC charter.

All statistical analyses will be performed using Statistical Analysis Software (SAS[®]) Version 9 or higher.

The following standards will be applied for the analysis unless otherwise specified. Data will be summarized descriptively by treatment and overall for each study phase. For the MAD phase, BOS161721 will be summarized overall and by each dose level, and placebo patients from each cohort will be combined. Select parameters will be summarized using patients from both study phases. Statistical testing will be performed on data from the Phase 2 study only.

Continuous data will be summarized using number, mean, standard deviation (SD), 25th and 75th percentiles, minimum, median, and maximum. Categorical data will be summarized by treatment group using frequency tables (number and percentage). Time to event data will be summarized using counts, medians, 25th and 75th percentiles, and standard error. All data will be listed for all patients.

Statistical inference will be based on a 2-tailed test with an overall 0.10 level of significance, unless stated otherwise.

The effects of noncompliance, background therapy use, treatment discontinuations, premature withdrawal from study and covariates will be assessed to determine the impact on the general applicability of results from this study. Exploratory analyses of the data will be conducted as deemed appropriate. Any deviations from the planned analyses will be described and justified in the final integrated CSR.

Protocol deviations and prohibited medications that define medication failures will be fully assigned and documented before database lock and unblinding.

Further details of the analysis, including the handling of missing data, transformations and other data handling procedures will be provided in the SAP.

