8.3 Interim Analysis and Power

One IA is planned for this study and will be conducted at the time of the POC decision for dose selection.

Since there is no IA during the POC phase, there is no impact on the type 1 error.

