	
To demonstrate a superior effect of BOS161721 at the chosen dose compared with placebo for response on clinical indicators of SLE activity, in adult patients with moderately to severely active SLE on limited background standard of care treatment
	
Secondary Efficacy Endpoints
 
 • The proportion of subjects with: 
 - SRI-4 response at each visit - SRI-5 and SRI-6 response (Section 6.3.4.2) - a sustained reduction of oral corticosteroid (CS) (≤ 10 mg/day and \leq Day 0 dose) between Day 120 and Day 210 - new BILAG A flare or > 1 BILAG B flares relative to baseline through Day 210 - PGA worsening - a BICLA response - a CLASI response - medication failures • Results and changes from baseline in: 
 - CLASI - swollen and tender joints ACR-28 - SLEDAI-2K - SLICC/ACR damage index • Time to medication failure • Duration of SRI-4 response • Time to first SRI-4 response • Time to BILAG A flare or > 1 BILAG B flare compared to baseline through Day 210 	
the analytical end to ensure SRI-4 responders meet all necessary criteria.

Safety			
	
 • To assess safety and tolerability of repeat doses of BOS161721 (20, 60, and 120 mg) administered SC in adult patients with moderately to severely active SLE on limited background standard of care treatment 	
Safety Endpoints
 
 • Incidence and severity of adverse events (AEs) and serious adverse events (SAEs), related AEs, AEs leading to study drug discontinuation, AEs by severity and relatedness • Injection site reactions • C-SSRS • 12-lead ECGs parameter results at each visit and change from baseline • Vital signs (blood pressure 	

Section	Description of Changes	Rationale
		[BP], heart rate, and temperature) parameter results at each visit and change from baseline 
 • Clinical laboratory results and change from baseline • Physical examinations changes from baseline • ADAs • Study drug exposure/compliance • Concomitant medication usage
Exploratory		

 • CCI [REDACTED] 	
 • CCI [REDACTED] 	

 • CCI [REDACTED] 	
 • CCI [REDACTED] 	

 • CCI [REDACTED] 	
 • CCI [REDACTED] 	

Section 3.1, Study Design

Replace:

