	
by-time interaction, baseline covariate, and covariate-by-time interaction. Normality will be assessed via diagnostic residual plots and Shapiro-Wilk statistic, but not as a formal statistical test of normality. If substantial departures from normality are observed, transformation will be used (eg, log and/or rank).
 
Details will be available in the SAP.
 
9.2.6.3 Population Pharmacokinetic Analysis or PK/PD Modeling
 
Plots of individual patient values for each relevant PD parameter on Y-axis and each relevant PK parameter on X-axis will be examined for relationship. If relationships are revealed by these diagnostic plots, PK and PD data from this study may be analyzed using modeling approaches to describe the relationship and may also be pooled with data from other studies to investigate any association between BOS161721 exposure and biomarkers or significant safety endpoints.
 
Details will be available in the SAP.
 
9.3 Interim Analysis and Power
 
Two IAs are planned for this study. The initial IA will be conducted at the time of the POC decision for dose selection.
 
The second IA will be performed for futility. IA2 is planned to be conducted at Day 90 when SRI-4 response is determined for approximately 60 patients (including all patients at the same dose level/matching placebo from the MAD study) after completing 3 months of treatment. The purpose of the IA2 is to assess if the trial could stop for an early futility conclusion, or continue. Since there is no plan to stop the trial for an early efficacy conclusion, there is no impact on the type 1 error. If that intention changes, then $p < 0.0001$ is required for an early efficacy conclusion at the IA2 in order to not impact the planned type 1 error level.
 
Nominal time profiles will be used for calculating PK parameters in the IA2. Details will be available in the SAP.
 
With:
	
8	STATISTICS	
	
The following analyses are planned:
 
An IA will be performed during the last cohort of the MAD phase to determine dose selection for the POC phase.The final analysis will be performed when all patients have completed the safety follow-up or withdrawn from the study.Safety analyses will be performed for DMC reviews throughout the study to evaluate dose escalation decisions and accumulating	
Updated to clarify that single alpha for a single primary hypothesis at a significance

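### Section 8.2.3 extends the primary superiority hypothesis at the 0.10 level to every secondary and exploratory endpoint; the level should be tied to the single primary SRI-4 test, which is itself correctly sized

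*Protocol*

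**What the plan says.** Section 8 sets the general level: "Statistical inference will be based on a 2-tailed test with an overall 0.10 level of significance, unless stated otherwise". It also restricts testing to one phase: "Statistical testing will be performed on data from the Phase 2 study only".

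Section 8.2.3 gives the decision rule for SRI-4 response at Day 210. If the BOS161721 response rate is the higher one, "then BOS161721 will be considered superior to placebo if the 2-sided p-value is less than or" equal to 0.10. The sentence that follows it is: "Secondary and exploratory endpoints for this POC study will be evaluated based on the same statistical hypothesis".

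The new Section 2 text, visible here only in the Appendix 7 summary of changes, words the secondary Phase 2 objective as a claim: "To demonstrate a superior effect of BOS161721 at the chosen dose compared with placebo for response on clinical indicators of SLE activity". The secondary endpoints listed beside it end with "Time to BILAG A flare or > 1 BILAG B flare compared to baseline through Day 210".

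Two further statements bear on the intended reach of the 0.10 level. The Appendix 7 rationale beside the new Section 8 says the text was updated to "clarify that single alpha for a single primary hypothesis at a significance" level is acceptable for a proof-of-concept study. Section 8.3 says: "Since there is no IA during the POC phase, there is no impact on the type 1 error".

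**The concern.** The recorded rationale confines the alpha to one hypothesis, but Section 8.2.3 does not. Directly after stating when superiority is declared, it carries the hypothesis over to all secondary and exploratory endpoints, and Section 8 offers no level other than 0.10 for testing them. The sections shown contain no testing order, no dependence on the primary result and no statement that the remaining p-values are nominal. The secondary objective is also written as something to be demonstrated.

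Followed as written, a trial that missed SRI-4 could still report superiority on BICLA, CLASI or time to flare, under a text that speaks of an overall 0.10 level. A reader of the study report could then take 10% as the error rate behind the whole set of claims.

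**Working it through.** **1. The plan's own figure.** Inputs from Section 8.1: 132 evaluable patients at 2:1, so 88 and 44; response 65% against 40%; two-sided 0.10; Pearson chi-squared.

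- Pooled rate: (88 × 0.65 + 44 × 0.40)/132 = 74.8/132 = 0.567.
- SE under the null: √(0.567 × 0.433 × (1/88 + 1/44)) = 0.0915.
- SE under the alternative: √(0.65 × 0.35/88 + 0.40 × 0.60/44) = 0.0897.
- Power: Φ((0.25 − 1.645 × 0.0915)/0.0897) = Φ(1.11) = 0.866.

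Exact enumeration gives 0.863, or 0.829 with a continuity correction. The stated power of more than 80% is reproduced.

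**2. Size of the primary test.** Exact enumeration of the Pearson test at 88:44:

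| Common response rate | Any two-sided rejection | False superiority |
|---|---|---|
| 40% | 0.099 | 0.049 |
| 50% | 0.097 | 0.048 |
| 65% | 0.103 | 0.053 |

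The primary test delivers its level, and testing other endpoints does not change that.

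**3. Number of secondary endpoints.** From the new Phase 2 endpoint list in Appendix 7:

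- 8 lines for proportions, or 9 if SRI-5 and SRI-6 are separated
- 4 lines for changes from baseline, or 5 if swollen and tender joints are separated
- 4 lines for times and durations

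That makes 8 + 4 + 4 = 16 to 9 + 5 + 4 = 18. SRI-4 by visit is counted once, and the redacted exploratory endpoints are left out. Adding the primary gives k = 17 to 19 tests.

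**4. Familywise rates with no true effect.** Under the Section 8.2.3 rule a false superiority finding has nominal probability 0.05 per endpoint, which is the favourable half of 0.10.

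- Independent, false superiority: 1 − 0.95^17 = 0.58; 1 − 0.95^19 = 0.62.
- Independent, any two-sided rejection: 1 − 0.90^17 = 0.83; 1 − 0.90^19 = 0.87.
- Correlated: simulation of equicorrelated normal statistics, 400,000 draws per setting.

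| Assumed correlation | At least one false superiority | At least one two-sided rejection |
|---|---|---|
| 0 | 0.58 to 0.62 | 0.83 to 0.87 |
| 0.3 | 0.41 to 0.43 | 0.75 to 0.78 |
| 0.5 | 0.32 to 0.33 | 0.62 to 0.65 |
| 0.7 | 0.23 to 0.24 | 0.45 to 0.47 |
| 0.8 | 0.18 to 0.19 | 0.36 to 0.38 |
| 0.9 | 0.13 | 0.27 |

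Leaving the primary out changes little: 16 to 18 independent secondaries give 0.56 to 0.60. The expected number of false superiority findings does not depend on the correlation: 17 × 0.05 = 0.85 to 19 × 0.05 = 0.95.

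**The case against.** The strongest reply is that the plan rests on one test, and that test is right. There is one primary endpoint, one dose against placebo and no interim analysis in the Phase 2 part, and the sample size concerns SRI-4 alone. This stands. A reader might infer from the familywise figures that the trial does not deliver its stated error rate; for the primary conclusion the document does not support that.

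Nor is *overall* ever defined as covering all endpoints. The superseded version carried two one-sided levels, so the word may simply mean one total two-sided level. This stands as well: the text is ambiguous, and it contradicts itself only if *overall* is read as familywise.

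The sentence on secondary endpoints names the hypothesis and does not repeat the threshold. That is literally so. But it follows the sentence that sets the threshold, and Section 8 gives no other, so p at most 0.10 is the natural reading.

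Unadjusted secondary testing is ordinary in a proof-of-concept trial, and a testing order could sit in an SAP that is not shown. Both are fair, and neither the lack of adjustment nor the lack of an order is the point. The point is a rule that the protocol does state, with no limit on the claim. An SAP that labelled these p-values nominal would still sit awkwardly beside it.

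Finally, the independent figure of 0.58 to 0.62 is unrealistic as a headline. SRI-4, SRI-5 and SRI-6 share components, and flare, medication failure and CLASI each appear in two forms. It should be read only as the upper end of the range.

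**Conclusion.** The concern holds in a limited form. The primary SRI-4 test is correctly sized, and its conclusion is not in question. What needs correcting is that Sections 8 and 8.2.3 together allow superiority to be claimed on every secondary and exploratory endpoint at the primary's level, against the recorded intent of one alpha for one primary hypothesis.

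Over the primary and the 16 to 18 listed secondaries, the chance of at least one false superiority finding runs from about 0.13 at correlation 0.9 to 0.58–0.62 under independence, against a nominal 0.05 per test. These figures assume no true effect on any endpoint, a common non-negative correlation chosen by the reviewer, and a count taken from the Appendix 7 list because the current Section 2 is not in the part shown. Splitting SRI-4 by visit, or adding the redacted exploratory endpoints, would enlarge the family. It is a cheap improvement in wording that changes what the trial may claim.

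**What to change.** - In Sections 8 and 8.2.3, state that the two-sided 0.10 level applies to the single primary test of SRI-4 response at Day 210.
- Replace the sentence in Section 8.2.3 that carries the hypothesis over with: secondary and exploratory endpoints will be reported with estimates, 90% confidence intervals and nominal p-values, without a confirmatory superiority claim.
- If the sponsor does want secondary superiority claims, prespecify instead a testing order that is conditional on the primary result.
- If the current Section 2 still words the secondary objective as demonstrating superiority, change it to evaluating the effect.

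The cost is wording only. All tests are still run, and sample size, power and the primary conclusion do not change. The one real loss is that, without a testing order, secondary results can no longer be described as demonstrated superiority.
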